2.5. SECONDARY ANALYSES

In addition, any observed values and changes from baseline for clinical and laboratory data, physical examination data, vital signs, pain and localised skin reactions will be summarised.

2.6. OTHER SAFETY OUTCOMES

2.6.1. SERIOUS ADVERSE EVENTS

The number of serious adverse events will be reported overall, and by classifications of severity, and relationship to study device and drug for the main analysis population.

The number and percentage of patients experiencing at least one serious adverse event will be reported overall, and for events classified by MedDRA System Organ Class and Preferred Term.

2.9.2 TREATMENT-EMERGENT ADVERSE EVENTS

Treatment-emergent adverse events are all events that occur after administration of the SQIN-Furosemide, regardless of causal relationship between the event and the SQIN-Furosemide. All treatment-emergent adverse events will be summarised in the same way as the serious adverse events with

the number of events reported overall and by classifications of severity, and relationship to study device and drug.

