SQIN-01: SQIN-Furosemide and SQIN-Infusor

SQI Inc.

An open label, single dose study to assess safety and efficacy of a novel patch infusor device and novel SUBCUTaneous furosemide formulation combination in patients with Heart Failure: a phase I clinical trial

Protocol

ACRONYM: SUBCUT-HF I

Protocol Version: 1.1
Date: 06/01/2021
EudraCT Number: 2020-005560-57
REC Reference Number: -----
Sponsor's Protocol Number:
Sponsor: SQ Innovation Inc.
Funder: SQ Innovation Inc.
IMP and medical device supplied by SQ Innovation Inc.
Host: NHS Greater Glasgow and Clyde and the University of Glasgow

This study will be performed according to the Research Governance Framework for Health and Community Care (Second edition, 2006) and The Medicines for Human Use (Clinical Trials) Regulations, 2004 SI 2004:1031 (as amended) and World Medical Association Declaration of Helsinki Ethical Principles for Medical Research Involving Human Subjects 1964 (as amended).

Confidentiality Statement

This protocol contains confidential information that must not be disclosed to anyone other than the sponsor, the Investigator Team, host NHS Trusts, regulatory authorities and members of the Research Ethics Committee. The study will be registered on EUDRACT and clinicaltrials.gov.

Study Synopsis:

Title of Study	An open label, single dose study to assess safety and efficacy of a novel patch infusor device and novel SUBCUTaneous furosemide formulation combination in patients with Heart Failure: a phase I clinical trial
Study Centre	1 site in Queen Elizabeth University Hospital in Glasgow
Investigational Product and Medical Device	The drug and device combination is called SQIN-01. SQIN-01 is a combination of SQIN-Infusor and SQIN-Furosemide Investigational pump (SQIN-Infusor, medical device) intended for subcutaneous infusion of investigational product, SQIN-Furosemide. SQIN-Furosemide is investigational subcutaneous furosemide formulation at 30mg/mL at pH 7.4 (range 7.0 to 7.8) intended for slow subcutaneous infusion using a biphasic delivery profile. 80mg of SQIN-Furosemide will be administered using SQIN-Infusor by subcutaneous infusion over 5 hours using biphasic delivery profile of 30mg in the first hour and 50mg over the remaining 4 hours.
Study Phase	I
Primary Objective	To investigate the safety, tolerability, efficacy and on-body performance of a novel patch infusor device and novel furosemide formulation combination (SQIN-01).

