Secondary Objective	To investigate the efficacy of SQIN-01 To investigate skin reactions and patient acceptability.
Primary Outcomes	
 • Safety as determined by treatment emergent adverse events (TEAEs), (including serious adverse events [SAEs]) and adverse drug events (ADEs)(including serious adverse drug events [SADEs]) • Infusion site pain measured using a Numerical Pain Rating Scale(1) (Appendix 3) • Any device failures (e.g. adhesive failure and drug delivery failure) • Serum furosemide concentration at 0, 60 and 240 minutes after start of SQIN-Furosemide infusion
Secondary outcomes	
 • Urine volume and sodium concentration in urine collected 8 hours after start of SQIN-Furosemide infusion • Presence of local skin reactions, recorded with photography and assessed using standardised erythema/edema assessment tool (2) (Appendix 4) • Patient acceptability using System Usability Scale(3) (Appendix 5)
Rationale	A new formulation of (neutral pH) furosemide (SQIN-Furosemide) that can be delivered subcutaneously by a pump placed on a patient abdomen has been developed. This trial will test the on-body performance of new subcutaneous pump device (SQIN-Infusor) and clinical efficacy of SQIN-Furosemide in patients with heart failure (HF).

Study design	Prospective, open-label, single dose study in 20 patients previously diagnosed with HF being treated with intravenous furosemide therapy at a dose of ≥ 40 mg/day as in-patients.
Sample Size	20
Screening	Coronary care unit and cardiology wards.
Main Inclusion Criteria	
 • Written informed consent • Male or female ≥ 18 years of age • Meet ESC criteria for diagnosis of HF(4) • Inpatient with a primary diagnosis of HF requiring treatment with intravenous furosemide at dose ≥ 40 mg/day per day

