2.9.3 NON TREATMENT-EMERGENT EVENTS

The non treatment-emergent events are all events that occur before the administration of the SQIN-Furosemide. These events will be summarised for the overall enrolled population in a similar way to the SAEs and treatment-emergent events.

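### The treatment-emergent window starts with the drug, but the main analysis population starts with the device, so device-phase adverse events are misclassified or left without a class

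*SAP*

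**What the plan says.** The SAP divides adverse events by their timing relative to the drug.

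- SAP 2.9.2: "Treatment-emergent adverse events are all events that occur after administration of the SQIN-Furosemide".
- SAP 2.9.3: "The non treatment-emergent events are all events that occur before the administration of the SQIN-Furosemide". On reporting it adds: "These events will be summarised for the overall enrolled population in a similar way to the SAEs and treatment-emergent events".

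The protocol synopsis describes a combined product, SQIN-01, whose drug is "administered using SQIN-Infusor by subcutaneous infusion over 5 hours". The primary objective concerns the combination, including how the device performs on the body.

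SAP 2.1 admits a patient to the main analysis population on consent, placement of the SQIN-Infusor and its activation. Receipt of drug is not a condition. The synopsis uses the same device-based set for its intention-to-treat analysis and treats patients who received the 80 mg dose as an additional analysis.

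SAP 2.4.1 gives the safety primary outcomes as TEAEs, adverse drug events and device failures, with infusion-site pain as a further primary outcome. SAP 2.6.1, under other safety outcomes, says "The number of serious adverse events will be reported overall" for the main analysis population and states no onset limit.

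**The concern.** Population and event window start at different moments. A patient enters the main analysis population through the device, but that patient's events become treatment-emergent only through the drug. Three consequences follow.

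1. Harm from placing or activating the device before drug flows is classed as non-treatment-emergent. It leaves the main-population TEAE tables and appears in a table for a different population.
2. A patient whose activated device delivers nothing has no administration for events to fall before or after. The protocol foresees this case: the synopsis gives failure of drug delivery as an example of a device failure.
3. Administration is a 5-hour process, and neither SAP section says which end of it counts.

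Safety is the first primary outcome listed, and the device is half of what is being tested. The event definition should follow the same exposure as the population. Two programmers should also reach the same classification from the text.

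**Working it through.** The check compares definitions. The plan gives no expected event rate, so there is no figure of its own to reproduce.

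**Inputs**

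- TEAE and non-TEAE rules: SAP 2.9.2 and 2.9.3.
- Main analysis population: SAP 2.1.
- Infusion: "biphasic delivery profile of 30mg in the first hour and 50mg over the remaining 4 hours" (protocol synopsis).
- Serum sampling at 0, 60 and 240 minutes from the start of infusion: SAP 2.4.1.
- Planned sample size of 20, chosen pragmatically: protocol synopsis.

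**Step 1. Infusion timeline.** 1 h + 4 h = 5 h = 300 min, and 30 mg + 50 mg = 80 mg. The description is internally consistent.

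**Step 2. Class of each event in a main-population patient under the two readings of administration**

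| Onset of event | Administration = start of infusion | Administration = end of infusion |
|---|---|---|
| After consent, before placement | Non-TEAE | Non-TEAE |
| After placement, before drug flow | Non-TEAE | Non-TEAE |
| During the infusion (0 to 300 min) | TEAE | Neither class |
| After the infusion | TEAE | TEAE |
| Any time after activation, no drug delivered | Neither class | Neither class |

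The second and last rows fail under both readings, so clarifying the word administration does not cure them. The third row fails only under the end-of-infusion reading.

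**Step 3. How much exposure the end-of-infusion reading would leave out.** All three serum sampling times fall before 300 min. Assuming a constant rate over the last 4 hours, the dose delivered by 240 min is 30 + 50 × 3/4 = 67.5 mg, and 67.5/80 = 84% of the total. A TEAE window opening after that point would make little sense, which is one reason to take the start as the intended meaning.

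**Step 4. Size per patient.** If all 20 planned patients reach activation, one patient whose only event changes class moves TEAE incidence by 1/20 = 5 percentage points. If 19 do, the step is 1/19 = 5.3 points. A patient who has another TEAE moves the event count but not the incidence.

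**Step 5. What remains captured elsewhere.** Adverse drug events, device failures and pain carry no after-administration condition in SAP 2.4.1. Skin reactions are listed under SAP 2.4.2 and summarised under 2.5. Serious events in a no-drug patient are counted under 2.6.1. What remains exposed is narrower: adverse events before drug flow that are not drug-related and not recorded as a device failure, pain score or skin reaction, and non-serious events of that kind in a patient who receives no drug.

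**The case against.** The strongest defence is that little is lost. Device failures and pain are primary outcomes in their own right, skin reactions are listed regardless of TEAE status, and TEAEs and SAEs are both broken down by relationship to device as well as drug. Events before administration are reported, only in another table. The analysis is descriptive, with no hypothesis test in the text seen. All of this stands, and it limits the point to the TEAE component.

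A reader might infer more in four places, and the documents do not support it.

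- *That events during the 300 infusion minutes are excluded from primary safety.* The before/after pairing makes sense as a complete split only if administration is a single moment, and the serum outcome is timed from the start of infusion. This is an ambiguity, not a planned exclusion.
- *That the primary safety outcome as a whole misses device events.* It does not, given the separate outcomes above.
- *That the 2.6.1 table contaminates the primary outcome with SAEs that predate exposure.* An SAE before infusion can appear in both 2.6.1 and 2.9.3. But 2.6.1 is an other-safety table, and the TEAE summary is separate.
- *That an adverse-device-effect outcome must be added beside* "adverse drug events (ADEs)(including serious adverse drug events [SADEs"*]).* Device relationship is already tabulated, so this is a preference.

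The defence does not answer the mismatch with SAP 2.1 or the patient who receives no drug.

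**Conclusion.** Wrong as written, within a limited scope. SAP 2.9.2 and 2.9.3 give a TEAE rule that does not match the main analysis population and misclassifies, or fails to classify, device-phase events in a study of a drug-device combination. The missing start or end of administration is a lesser, wording-level fault.

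The total size is unknown: the documents give neither event rates nor the interval between placement and drug flow. The 5 points per patient assumes a denominator of 20 and that the reclassified event is that patient's only one.

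The conclusion also assumes that no clarifying definition sits elsewhere. This review saw only the synopsis of the protocol and the SAP from section 1.6.6 onward. However, 2.9.2 and 2.9.3 are themselves the defining sections.

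**What to change.** In SAP 2.9.2, define a TEAE as any event with onset or worsening at or after the start of SQIN-Infusor placement, whether or not drug is delivered, summarised in the main analysis population. In 2.9.3, define non-treatment-emergent events as those from consent to before placement. This covers the no-drug patient and removes the start-or-end question.

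Add one sentence saying where post-placement events are listed for a patient whose device is placed but never activated, since that patient is outside the main analysis population. Optionally, flag each SAE in the 2.6.1 table as before or after placement.

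The cost is SAP wording. The present before/after split already needs event timing; the new one needs the time of placement, which is assumed to be recorded. The TEAE count may be slightly higher. The primary outcomes in the protocol synopsis need not change.

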2. ANALYSIS

2.1. STUDY POPULATIONS

The main analysis population will be all subjects who consented and were placed on the SQIN-Infusor and it was activated in accordance with the instructions.

We will also look at the enrolled population, which is all subjects that have consented into the study and meet the entry criteria.

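### Treatment-emergent events in SAP 2.9.2 are dated from the drug alone, so some non-serious device harm falls outside the primary treatment-emergent outcome of a drug-device combination

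*SAP*

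**What the plan says.** The protocol synopsis describes a combination product: "SQIN-01 is a combination of SQIN-Infusor and SQIN-Furosemide". Its primary objective covers the safety, tolerability and on-body performance of that combination.

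SAP 2.1 defines the main analysis population by the device: "all subjects who consented and were placed on the SQIN-Infusor and it was activated in accordance with the instructions". Delivery of drug is not a condition.

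SAP 2.9.2 defines treatment-emergence by the drug. The term covers "all events that occur after administration of the SQIN-Furosemide", whether or not the drug caused them. The same section has these events counted by severity and by relationship to device and to drug. SAP 2.9.3 gives the complement: "The non treatment-emergent events are all events that occur before the administration of the SQIN-Furosemide". On reporting, it adds: "These events will be summarised for the overall enrolled population in a similar way to the SAEs and treatment-emergent events".

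In both documents, the primary outcome headed safety consists of treatment-emergent adverse events and adverse drug events. It has no term for adverse device events. Device failure is a separate primary outcome, which the protocol words as "Any device failures (e.g. adhesive failure and drug delivery failure".

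**The concern.** The exposure that puts a subject in the denominator is the pump. The exposure that lets the subject's events count as treatment-emergent is the drug. For most subjects these nearly coincide, but they separate in two situations: the interval between placing the pump and the first flow of drug, and a pump that is activated but delivers nothing.

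The SAP wants the treatment-emergent table to show device-related events, since it asks for that classification in 2.9.2. A window that only the drug can open cannot show them all. What is at stake is whether the first primary outcome, in a first-phase study of a new pump, counts all non-serious harm from the pump.

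A smaller wording matter sits alongside. The infusion lasts 5 hours, and 2.9.2 does not say whether its window opens at the start or the end of administration.

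**Working it through.** The plan states no rate, power or effect size on this point (the 20 subjects are a pragmatic number), so there is no figure to reproduce. The check is to take each case through the definitions.

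**Inputs.** Main population: SAP 2.1. Treatment-emergent and non-treatment-emergent rules: SAP 2.9.2 and 2.9.3. Primary outcomes and listing: SAP 2.4.1 and the protocol synopsis. Other outputs: SAP 2.4.2, 2.5 and 2.6.1.

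**Classification of a non-serious, device-caused event**

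| Case | In main population? | After drug administration (2.9.2)? | Before drug administration (2.9.3)? | Result |
|---|---|---|---|---|
| A. Drug has started to flow | Yes | Yes | No | Treatment-emergent |
| B. Pump placed, drug not yet flowing, drug given later | Yes | No | Yes | Non-treatment-emergent |
| C. Pump delivers part of the dose, then stops; event after flow began | Yes | Yes | No | Treatment-emergent |
| D. Pump activated, no drug delivered at all | Yes | No | No, as there is no administration to precede | Neither |
| E. Pump placed, never activated, no drug | No | No | No, for the same reason | Neither |

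Rows A and C read 2.9.2 as dating from the start of administration.

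In B and D the subject belongs to the main population and the event is not in the treatment-emergent outcome. By its name, an adverse drug event would not include harm caused by the pump before or without drug, so the other half of the primary safety outcome does not appear to capture it. That step is an inference, because no definition of adverse drug event is in the text available.

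**What other outputs still capture**

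- Device failures: separate primary outcome, listed by subject (2.4.1). This records the malfunction, not necessarily the resulting harm.
- Infusion site pain: separate primary outcome (2.4.1), not tied to the treatment-emergent rule.
- Local skin reactions: listed (2.4.2) and summarised (2.5).
- Serious adverse events: counted in the main population with no drug-timing limit (2.6.1).
- Case B events: summarised in the enrolled population (2.9.3), in a format like that of 2.9.2, which splits by relationship to the device.

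The residue is non-serious device harm that is not a pain score, a skin reaction or a device failure, and that arises in case B or D.

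**Scale.** One affected subject is 1/20 = 5% of the planned sample. The documents give neither the frequency of such events nor the time from placement to flow. As an illustration only, let p be an assumed per-subject probability of being affected. With 20 independent subjects, the chance of at least one is 1 − (1 − p)^20, and the expected number is 20p:

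| Assumed p | Chance of at least one | Expected subjects |
|---|---|---|
| 1% | 18% | 0.2 |
| 2.5% | 40% | 0.5 |
| 5% | 64% | 1 |
| 10% | 88% | 2 |
| 20% | 99% | 4 |

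The table shows how often the question would arise under each assumption. It does not estimate the size of any bias.

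**The case against.** The strongest reply is that little is lost. Adhesive and delivery failures are already primary, as is infusion site pain. Skin reactions are listed, serious events are counted whenever they occur, and pre-drug events appear in a table that should still show their relationship to the device. All of this stands, and it makes the gap narrow. It does not close it: none of these outputs restores the event to the treatment-emergent count, and case D events are assigned to no adverse event table unless serious.

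A reader might infer more than the text supports, in five ways:

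- *That 2.9.3 classes events as non-treatment-emergent when no drug flows.* It does not. With no administration there is no before or after, and the events are unassigned.
- *That every drug delivery failure removes a subject from the treatment-emergent count.* The documents do not define that failure as zero delivery. A pump that stops part-way has administered drug (case C).
- *That the rule flatters the device overall.* A pump that delivers nothing should itself be recorded against the device, as a primary device failure. Only the treatment-emergent count is affected.
- *That a percentage bias can be stated.* That would need an event rate and a number of non-delivering pumps, and the documents give neither.
- *That events during the 5-hour infusion are excluded.* Read together, 2.9.2 and 2.9.3 split time into before and after, which most naturally means the start of administration. Saying so is a drafting improvement.

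Finally, the text available is the protocol synopsis and the SAP from section 1.6.6 onward, so a fuller definition elsewhere cannot be excluded.

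**Conclusion.** The point holds in a limited form. As written, the treatment-emergent window is opened by the drug, whereas the product, the main population and the required causality classification all include the device. Non-serious device harm before drug flow is classed as non-treatment-emergent; in a main-population subject who receives no drug it is assigned to neither category. Both fall outside the primary treatment-emergent outcome, and any omission can only lower that count.

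The loss cannot be sized from the documents. It is probably small in number: the placement-to-flow interval may be short, and only complete non-delivery matters in the second case. The conclusion rests on the literal wording of SAP 2.9.2 and 2.9.3 and assumes that no other definition in the full documents overrides it. It is worth correcting because safety of the combination is the first primary outcome and the correction is simple.

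**What to change.** - **SAP 2.9.2:** define a treatment-emergent event as one with onset at or after placement of the SQIN-Infusor, including during the infusion, and whether or not drug is delivered. Keep relationship to device and relationship to drug as separate attributes.
- **SAP 2.9.3:** define non-treatment-emergent as onset before placement.
- **Subjects with a pump placed but never activated:** state that their events are reported in the enrolled-population summary. Without this, dating from placement would make their later events treatment-emergent, while the listing in 2.4.1 covers only the placed-and-activated population, so those events would appear in neither place.
- **Listing:** add a flag for onset phase, namely placement to start of drug flow, during infusion, or after infusion. Readers who want the drug-dated count can then recover it.

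The cost is a few sentences of SAP text and one listing column, with onset recorded finely enough to assign the phase. The sample size does not change. The treatment-emergent count may come out slightly higher.

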2.9.3 NON TREATMENT-EMERGENT EVENTS

The non treatment-emergent events are all events that occur before the administration of the SQIN-Furosemide. These events will be summarised for the overall enrolled population in a similar way to the SAEs and treatment-emergent events.

3. DOCUMENT HISTORY

This is version 1.0 of the SAP for the SUBCUT-HF Phase I study, dated 19/04/2021.

4. TABLE SHELLS

Table 1.1: Study Disposition	
	All
Consented	N
Screen Failures	N (%)
Screen failure reason 1	N (%)
Screen failure reason 2	N (%)
.....	N (%)
Enrolled population (consented and met eligibility criteria)	N
Main analysis population (activated SQIN-Infusor)	N
Completed the study	N (%)
Early termination	N (%)
Reason for early termination	
Adverse Event	N (%)
Subject withdrew consent	N (%)
Withdrawn by investigator	N (%)
Withdrawal by Sponsor	N (%)
